**NCT #:** **NCT05871151**

**Document date:** **7/31/2025**

**Patient Population:**

\*\*We will recruit, screen, and enroll up 20 subjects in this study.

**Inclusion Criteria:**

1. 1. Diagnosis of Parkinson's Disease by a board-certified Neurologist, or by a Nurse Practitioner or Physician Assistant under the supervision of a Neurologist.
2. 2. Age between 35 and 80 years
3. 3. No walking aids
4. 4. Stable medication 4 weeks prior to the study
5. 5. No falls in the past 6 weeks
6. 6. Must have a neurologist or movement disorder specialist willing to approve and monitor their participation in the 'off' state' period of the study\*\*

**\*\*Clinically Defined "Off" State:** Patients with Parkinson's disease have motor and cognitive fluctuations that can impact the interpretation of assessments performed in different medication states. To address this, we will conduct the initial evaluation in the practically defined off medication state, defined as when the participants have refrained from taking their PD medications for a period exceeding 12 hours. In this off medication state, we aim to observe and measure changes in the cardinal PD symptoms: tremor, rigidity, bradykinesia, and dyskinesias. These observations will be made using the physical and cognitive assessments described below. This approach is vital to our study as it allows us to investigate the effects of the intervention in isolation. To mitigate any potential discomfort or adverse effects, this will be done under the careful supervision of our clinical team, which is supervised by [name], who is a neurologist specializing in the treatment of individuals with Parkinson's Disease. Additionally, we will obtain consent from the participants provider to ensure that they are safe to withhold PD medications for 12 hours prior to enrolling the participant in our study. *To further ensure participant safety, we will require that the participant has someone drive them to and from their clinic visits when they are in the clinically defined off state.* We will ensure participant safety and comfort throughout the evaluation sessions, intervening immediately if any adverse effects are observed. By focusing on the clinically defined 'off' medication state, we hope to gain a clearer understanding of the standalone effects of the brain stimulator on the symptoms and progression of Parkinson's disease. The findings of this study may contribute to future developments in the management and treatment of this debilitating condition.

**Exclusion criteria:**

1. 1. Moderate-severe cognitive impairment (MoCA <20)
2. 2. Diagnosed severe depression
3. 3. Antidepressive or antipsychotic medication
4. 4. Participation in a VNS study in the past year
5. 5. Disabling bradykinesia to ensure patients are able to participate in intensive physiotherapy (based on clinical impression and in accordance to UPDRS part III item 14 - to be administered in clinic)
6. 6. Prior history of cardiovascular, neurological or musculoskeletal disorders known to interfere with testing PD features
7. 7. Implanted medical device of any type, (8) history of seizures, (9) peripheral neuropathy including temporal mandibular disorders and Bells Palsy
8. 8. Vasovagal syncope.

9. 9. Pregnancy
10. 10. non-English speaking

### **Screening & Informed Consent**

- Participants who have been deemed eligible for this study will attend an in-person session at either UAB SRC room R027, Community Health-19 building, or at Lakeshore.
- Upon arrival, the study coordinator/designated personnel will perform a more in depth screen for eligibility
- The participant must also pass cognitive screening (MoCA) and a motor screen (MDS-UPDRS Part III), however this will be completed after informed consent.
- If eligible, the study coordinator/designated personnel will consent the participant, using the Informed Consent form
- After informed consent has been obtained, the participant will undergo cognitive screening using the Montreal Cognitive Assessment. The Montreal Cognitive Assessment (MoCA) is a brief screening test that assesses various cognitive domains, including attention and concentration, executive functions, memory, language, visuoconstructional skills, conceptual thinking, calculations, and orientations. The MoCA is used to detect mild cognitive impairment (MCI), a condition that can precede the onset of dementia and monitor changes in cognitive function over time. If the participant scores <25/30 on this assessment, they will be excluded from the study.
- -After informed consent, the participant will also undergo motor screening using the MDS-UPDRS Part III. The Movement Disorder Society's Unified Parkinson's Disease Rating Scale (MDS-UPDRS) Part III is a comprehensive clinical assessment tool designed to evaluate the motor function in patients with Parkinson's disease. This segment of the scale involves a clinician-scored evaluation of motor skills, which includes assessments of speech, facial expressions, tremors, rigidity, finger dexterity, hand movements, rapid alternating movements, leg agility, arising from a chair, posture, gait, postural stability, and body bradykinesia. The UPDRS will be administered by a Movement Disorder Society-certified assessor. If the participant has disabling bradykinesia based on clinical impression and in accordance to UPDRS part III item 14, they will be excluded from the study.
- Each participant that is eligible for the study will undergo a 5-minute trial of taVNS (after obtaining consent) to ensure that they can tolerate the intervention. If they are unable to tolerate the intervention, they will be excluded from the study.
- At the conclusion of this session, participants will be scheduled for an Initial Assessment visit. See below for details.

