### **Randomization Protocol:**

- To ensure that randomization is blinded, we will use a computer-generated randomization sequence.
- After obtaining informed consent, we will randomize eligible participants into one of two groups.
  - GROUP 1: active taVNS + exercise (details provided below)
  - GROUP 2: non-active taVNS + exercise (details provided below)

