#### **Treatment (over the course of 4-6 weeks, 1 hour sessions, up to 3 sessions/week)**

- During treatment clinic visits, participants who are randomized into the **active taVNS + exercise** group will receive 15 minutes of active taVNS prior to treatment.
- Participants who are randomized into the **non-active taVNS + exercise** group will receive 0 mA of current for 15 minutes prior to treatment.
- To implement the non-active condition, participants will still undergo the same electrode placement procedure as those in the active taVNS group, with the electrodes placed in the ears. However, the taVNS device will be set to a 0 mA (no stimulation) during the non-active condition. Participants will be informed prior to the stimulation that they may or may not feel anything during the session, and that just because they do not feel anything does not mean that they are not receiving stimulation.

- All participants will be guided through low intensity, high amplitude exercises led by a trained exercise specialist.
- The exercise intervention proposed involves the supervision of a trained exercise specialist at all times during the treatment session
- The use of a gait belt will further ensure the participant's safety by providing additional support and stability during exercise
- The proposed exercise intervention will be conducted by a trained exercise specialist who has expertise in assessing and managing potential risks associated with exercise interventions. This will ensure that the intervention is safe for the participant and will minimize the risk of injury or adverse events
- After each treatment session, participants will be asked post-intervention questions to evaluate potential side effects of the taVNS treatment and exercise (see below):
  - 1. Since our last session, have you experienced any unusual physical symptoms such as dizziness, fatigue, muscle soreness, shortness of breath, or heart palpitations?
  - 2. Have you experienced any unusual discomfort or pain in the ear where the taVNS device was applied?
  - 3. Have you noticed any changes in your skin around the area where the taVNS device was applied, such as redness, swelling, or rash?
  - 4. Have you felt any changes in your mood, like feeling more anxious, depressed, or irritable since the last session?
  - 5. Have you noticed any changes in your ability to concentrate or remember things?

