  - 6. Have you experienced any other side effects or symptoms that you believe may be related to the taVNS treatment or exercise program?
- If a participant reports experiencing any adverse effects, they will be advised to seek appropriate medical attention. We will also document all reported side effects.
- Participants will wear a heart rate monitor during each treatment session to monitor and record heart rate response to exercise.
- Participants will be asked to answer a series of questions about the tolerability of the taVNS treatment & exercise intervention via a RedCap survey.

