### Re-Assessment (2 hours)

\*\*Prior to the re-assessment, enrolled participants will receive an email from the study coordinator outlining the requirements of the clinically defined "off" state.

- All participants will complete outcome measure assessment after completion of the protocol, including re-administration of the Montreal Cognitive Assessment (**MoCA**), Movement Disorder Society-Sponsored Revision of the Unified Parkinson's Disease Rating Scale(**MDS-UPDRS**), 6-minute walk test (**6MWT**), mini-Balance Evaluation Systems Test (**Mini-BESTest**), Functional Gait Assessment (**FGA**), the modified Clinical Test of Sensory Integration and Balance (**mCTSIB**), Delis-Kaplan Executive Functioning System (**DKEFS**), Digit span test (DST), Digit symbol substitution test (DSST), Flanker test, **PROMIS-NeuroQOL**, the Short Form-36 (**SF-36**)
- Additionally, participants will complete a qualitative interview to assess tolerability and feasibility of the treatment provided in this study. The interview will be recorded and transcribed on a HIPPA compliant platform and will be stored in a secure database. Audio and transcription will be analyzed at the conclusion of the study.
- Participants will be asked to answer a series of questions about the tolerability of the taVNS treatment & exercise intervention via a RedCap survey.

*Participants will be compensated with a \$100 clincard at the conclusion of this visit.*

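### Does giving every participant a 5-minute taVNS tolerance trial, followed by a 0 mA control, leave a gap in feasibility reporting or masking that the plan must fill?

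*Combined protocol and SAP*

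**What the plan says.** The screening session ends with a tolerance step: every eligible participant "will undergo a 5-minute trial of taVNS (after obtaining consent) to ensure that they can tolerate the intervention". The consequence of failing is explicit: "If they are unable to tolerate the intervention, they will be excluded from the study". The session then closes with scheduling of the Initial Assessment. The next section, Randomization Protocol, states: "After obtaining informed consent, we will randomize eligible participants into one of two groups".

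In the Treatment section, the control arm has the electrodes but no current: "However, the taVNS device will be set to a 0 mA (no stimulation) during the non-active condition". Two features protect masking. Controls' electrodes are handled identically ("participants will still undergo the same electrode placement procedure as those in the active taVNS group"), and there is a script ("Participants will be informed prior to the stimulation that they may or may not feel anything during the session"), which adds that absence of sensation does not imply absence of stimulation.

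Tolerability is collected through "questions about the tolerability of the taVNS treatment & exercise intervention via a RedCap survey", and at Re-Assessment "participants will complete a qualitative interview to assess tolerability and feasibility of the treatment provided in this study". Statistical Analysis tracks recruitment, retention, adverse events and compliance, adds patient feedback on acceptability and usability, and estimates effect sizes from group means. Patient Population caps the study at 20.

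**The concern.** There are two separate worries.

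The first is feasibility. The survey and the interview reach only people who passed the tolerance trial, so they describe a group already selected for tolerance. If the failures were never reported, a later trial would not know how many people could not manage five minutes. The trial and randomization are each timed only as following consent, and people are called eligible before the trial. On a literal reading, a failure could therefore occur after allocation and become a post-randomization exclusion.

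The second is masking. A control who felt current in the trial could notice its absence at every later session. The effect sizes cover self-reported outcomes (NeuroQOL, SF-36) and effort-dependent ones (6MWT, timed cognitive tests), which expectation could shift. No described instrument asks participants which group they think they were in.

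**Working it through.** The plan states no power, effect size, failure rate or allocation ratio, so there is no figure to reproduce. Apart from the cap of 20, every count below is assumed.

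**Order.**
- The tolerance trial is the last exclusion step under Screening & Informed Consent, and randomization follows under its own heading.
- Calling people eligible beforehand decides little, because that section uses the word loosely. People are deemed eligible before they attend and again before consent, yet the MoCA and motor exclusions still come afterwards.
- Those two screens are also timed only as after consent. A reading that puts the tolerance trial after randomization would put them there too, which is not how a screening section is normally read.
- Under that less natural reading, and with an assumed 10:10 split, two failures unrelated to arm would fall in the same arm with probability 2 × C(10,2)/C(20,2) = 2 × 45/190 = 0.47. This figure depends wholly on that reading and that split, so it carries no weight.

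**Failure count.**
- If true intolerance were 5%, 10% or 20%, the chance of at least one failure among 20 starters would be 1 − 0.95^20 = 0.64, 1 − 0.90^20 = 0.88 or 1 − 0.80^20 = 0.99. Some failures are therefore plausible.
- Exact (Clopper-Pearson) 95% intervals are 0% to 17% for 0/20, 1% to 32% for 2/20 and 6% to 44% for 4/20.
- The count comes from screening records and needs no new data item. A screen failure with its reason is an ordinary line of recruitment reporting, and symptoms during the trial would ordinarily be reported as adverse events.

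**Does selection distort a tolerability rate?**
- Suppose 2/20 fail and 9/9 active participants tolerate treatment. The on-treatment figure is 9/9 = 100% (66% to 100%), and the pass figure is 18/20 = 90% (68% to 99%).
- The first concerns 15-minute sessions and the second a single 5-minute trial. They are different quantities with nearly the same interval. The plan also defines no tolerability rate that could be biased. The contrast shows no distortion.

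**Cap.**
- If failures count toward 20, then 20 − 2 = 18 or 20 − 4 = 16 remain.
- With an equal split and unchanged SD, standard errors grow by √(20/18) = 1.05 or √(20/16) = 1.12, that is, by about 5% or 12%. No power target is breached, because none is set.

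**Masking check, assumed 10 per arm.**
- Exact 95% intervals for the share guessing a given group are 19% to 81% for 5/10 and 44% to 97% for 8/10.
- Guesses of non-active by 8/10 in each arm give a difference of 0 with a Newcombe 95% interval of −34 to +34 points. Even identical answers would leave masking unresolved.
- Guesses by 8/10 of controls against 3/10 of active participants give a difference of 50 points (7 to 74). Only a gap of about that size would stand out.

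**The case for a change.** The strongest case for a change is that a feasibility study is the place to learn about intolerance and about how the control performs. The proposal is also cheap: one table row, one survey item and two sentences, with no extra visit and no change to stimulation. The electrode procedure and the script are meant to preserve masking; they do not measure whether it held. Imprecise data are better than none, and a 50-point gap would be informative.

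Much of this is fair. It is true that neither recruitment nor adverse events is defined to include trial failures, and that no guess question is described. It would be good practice for the report to give the number intolerant over the number who started, apart from on-treatment tolerability. That is reporting, however, and can be done from screening records under the plan as it stands.

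On masking, that the trial current was active and felt is an inference. The survey items and interview guide are not reproduced, so the absence of a guess item cannot be fully established. The post-session questions on ear discomfort and skin changes go to both arms and give some indirect information about sensation. A guess at Re-Assessment may reflect perceived benefit, so even a large gap would not isolate sensation. It may also prompt thoughts about allocation before the Follow-up outcomes are measured. It would set no threshold and would not adjust any effect size.

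**Conclusion.** No change to the plan is needed. The order of the tolerance trial, the counting of failures and the treatment of the cap are small gaps in a short plan. The section layout and usual screen-failure reporting fill them sensibly. The scenarios that make them look serious depend on an unnatural reading of the sequence or on comparing unlike quantities with assumed counts.

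The allocation guess is a trade-off on which statisticians can reasonably differ. It corrects no stated rule or figure and changes no estimate, and at about 10 per arm it could leave a difference uncertain by 34 points either way. The sponsor may add such an item by choice, but leaving it out is not an error.

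This conclusion assumes that screening records note tolerance failures and that the trial precedes allocation, as the layout implies. The size of any expectation effect cannot be derived from the documents, and none is claimed.

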### **Randomization Protocol:**

- To ensure that randomization is blinded, we will use a computer-generated randomization sequence.
- After obtaining informed consent, we will randomize eligible participants into one of two groups.
  - GROUP 1: active taVNS + exercise (details provided below)
  - GROUP 2: non-active taVNS + exercise (details provided below)

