**Statistical Analysis:**

To assess feasibility, we will track recruitment rate, retention rate, adverse events, and compliance. We will obtain patient feedback to gather insight about the acceptability and usability of this intervention. We will perform paired t-tests to compare the mean outcome measure values of the treatment and control groups to estimate effect size.

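### The plan states no allocation ratio, blocking, stratification or baseline adjustment, so in at most 20 people neither arm size nor baseline severity is protected from chance imbalance

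*Combined protocol and SAP*

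**What the plan says.** All references are to the combined protocol and SAP.

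- **Size (Patient Population):** "We will recruit, screen, and enroll up 20 subjects in this study". This is a ceiling. People can also leave between consent and allocation, on the cognitive screen, the motor screen or the tolerance trial of the stimulator: "If they are unable to tolerate the intervention, they will be excluded from the study".
- **Allocation (Randomization Protocol):** "To ensure that randomization is blinded, we will use a computer-generated randomization sequence". The section continues: "After obtaining informed consent, we will randomize eligible participants into one of two groups". It then lists active and non-active stimulation, each with exercise. No ratio, block size, stratification factor, minimization or list holder is stated there or elsewhere.
- **Severity score (Screening & Informed Consent):** "After informed consent, the participant will also undergo motor screening using the MDS-UPDRS Part III". It serves as an eligibility check. No medication state is given for it. The instructions about the off state are sent before the Initial Assessment, the Re-Assessment and the Follow-up, and Part III is measured at each of those visits.
- **Analysis (Statistical Analysis):** "We will perform paired t-tests to compare the mean outcome measure values of the treatment and control groups to estimate effect size". No covariate or baseline value is named.

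**The concern.** The only stated property of the sequence is that a computer generates it. A run of independent coin flips would comply, and so would a blocked list. In a trial this small the two behave differently, and a reader cannot tell which is meant.

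Two things are at stake. The first is arm size: a lopsided split makes the effect-size estimates less precise than the same number of people could give. The second, and larger, is severity. The MDS-UPDRS Part III, the walk tests and the balance and gait scales all measure motor function, so a chance difference in severity between arms would plausibly push many outcomes the same way and could be read as a treatment effect, or hide one. Part III is collected before treatment in any case, yet the plan uses it neither to balance the arms nor to adjust the comparison.

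**Working it through.** The plan gives no sample-size justification and no imbalance figure, so there is no figure to reproduce.

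**Inputs.** n = 20 is the ceiling in Patient Population. The 1:1 ratio and simple (coin-flip) allocation are assumptions. n = 12 is an illustration of under-enrolment.

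**1. Arm sizes under simple 1:1 allocation.** X, the number in one arm, is Binomial(n, 0.5). For n = 20, 2^20 = 1,048,576.

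- 10:10: C(20,10)/2^20 = 184,756/1,048,576 = 0.176, so unequal arms have probability 0.824.
- 11:9: 2 × 167,960/1,048,576 = 0.320. Hence 12:8 or worse = 0.824 − 0.320 = 0.503 (unrounded terms).
- 12:8 exactly: 2 × 125,970/1,048,576 = 0.240. Hence 13:7 or worse = 0.263.
- 13:7 exactly: 2 × 77,520/1,048,576 = 0.148. Hence 14:6 or worse = 0.115.
- With n = 12, 8:4 or worse: 2 × 794/4,096 = 0.388.

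**2. What a split costs.** Relative efficiency of an a:b split is 4ab/(a+b)², and SE inflation is one over its square root.

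| Split | Relative efficiency | SE inflation |
|---|---|---|
| 11:9 | 0.99 | 0.5% |
| 12:8 | 0.96 | 2.1% |
| 13:7 | 0.91 | 4.8% |
| 14:6 | 0.84 | 9.1% |

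The average over all splits is (n − 1)/n = 19/20 = 0.95, a loss of 5%.

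**3. Severity imbalance at exactly 10:10.** In SD units the baseline difference has standard error √(1/10 + 1/10) = 0.447. By the normal approximation, P(|difference| > 0.5 SD) = 2[1 − Φ(0.5/0.447)] = 0.264. As a cross-check, suppose 10 of the 20 are more severe. The chance that they divide 7:3 or worse between the arms is 2 × (1 + 100 + 2,025 + 14,400)/184,756 = 0.179.

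If baseline and final scores correlate at ρ, a 0.5 SD baseline gap moves the expected final difference by 0.5ρ SD. The documents do not give ρ; over its range from 0 to 1 the shift runs from 0 to 0.5 SD.

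**4. What the changes achieve.** With blocks of 2 and 4 in random order, the arms never differ by more than two people, so n = 20 ends at 11:9 or better. This leaves the 0.264 in step 3 essentially unchanged, because that figure already assumes equal arms. Including the baseline score in the model addresses it, at a cost of one residual degree of freedom (20 − 2 = 18 becomes 20 − 3 = 17).

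Two severity strata would allow a difference of up to two in each, hence up to four overall: 12:8 at worst with n = 20.

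**The case against.** The case on the other side has several parts.

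- **Silence is not a choice.** A reader might infer that the plan uses an unrestricted sequence. It does not say so. Blocked lists are computer-generated too, so every arm-size figure above is conditional. This stands.
- **Unequal is not the same as harmful.** A reader might take from step 1 that the arms will be unequal more than 80% of the time and treat that as the problem. The figure is 82.4% at n = 20 under simple 1:1 allocation; it is 77.4% at n = 12 and falls below 80% at every even n of 14 or fewer. It also counts 11:9, which costs 1% of efficiency. In a feasibility trial with no stated power target, a 5% average loss is minor. This stands.
- **Safety by arm.** A reader might argue that a small arm leaves too few people for its safety and retention data. The Statistical Analysis section says these will be tracked but does not say by arm, so the documents do not support that as a stated aim.
- **Chance imbalance is not bias.** Randomization is fair on average, and the standard error of a valid unadjusted comparison already includes this variation. True, but the estimate from this one small trial can still be displaced, and adjustment recovers precision at little cost.
- **The t-tests may already use baseline.** Paired could mean before against after within a person. The sentence, however, describes a comparison of treatment and control means and names no baseline or change score, so this cannot be assumed.
- **The screening score may be unsuitable.** Its medication state is not given, and the protocol itself warns that medication state affects interpretation. This stands, and favours the Initial Assessment score.
- **Small blocks are predictable.** Someone must set the device to 0 mA, and the plan does not separate that person from enrolment. Simple randomization is a defensible protection against guessing. This is a real trade-off, which varied block sizes and an outside list holder reduce but do not remove.

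**Conclusion.** The point holds as a gap in specification with a cheap remedy. As written, the plan permits coin-flip allocation followed by an unadjusted comparison.

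The arm-size part is modest. It rests on assumed simple 1:1 allocation of 20 people, and if the sponsor already intends blocks, one sentence settles it. The severity part carries more weight because it does not depend on how the list is generated, short of balancing on severity: about a one-in-four chance of a gap above 0.5 SD, taking equal arms of 10 and a roughly normal mean difference. Blocking alone would not cure it.

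The documents do not support saying that allocation is unrestricted, or that imbalance will seriously damage precision.

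**What to change.** 1. **Randomization Protocol.** State a 1:1 ratio and permuted blocks of randomly varied size, for example 2 and 4. State that the list is generated and held by someone outside the study team, who releases each allocation only after eligibility is confirmed.
2. **Statistical Analysis.** Compare the arms with a linear model for each outcome that includes arm and baseline MDS-UPDRS Part III. Use the off-state score from the Initial Assessment, and record it before the allocation is revealed to the assessor. Report the adjusted difference with its confidence interval.
3. **Optional.** Stratify on one two-level split of the screening Part III score, fixed in advance, and include the stratum or the score in the model. At this size, use no more than this one factor.

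**Cost.** A program setting, a few sentences, an outside list holder and one degree of freedom; no new assessment is needed. The remaining downside is that staff who set the device, and so learn past allocations, may guess the end of a block. The optional stratification gives up some control of overall arm size.
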